### 7.6 Methods for Clinical Procedures

#### Assessment of lung nodules with low dose CT scan at IEO

Investigations will be performed with low-dose CT scans (average effective dose  $<1.5$  mSv, without contrast medium), with a multidetector (64 slices) CT scanner (CT750 HD/Optima 660, General Electric Healthcare, USA) with the following parameters:

- 120 Kvp, 30 mA
- Matrix 512x 512
- pitch 1.75
- 2.5 mm thickness
- Soft tissue algorithm
- single breath, in respiratory apnoea
- retro-reconstruction at 1.25 mm interval
- at the end of a session of 15 - 20 subjects the investigations will be sent to the workstation and archived both on hard-disk and on CD in DICOM format.

- multiplannar reconstruction and 3-dimensional volume reconstruction will be performed on the workstation (Advantage Windows 4.2, General Electric medical system)

Nodule volumes and volume doubling time (VDT) will be automatically calculated by Lung VCAR specific software (GE healthcare). In absence of available volumetry by the software, VDT will be calculated by the following formula using the maximum diameter.

$$VDT = \frac{\log_{10} 2 \times (\text{difference in days between first CT and second CT})}{3 \times \log_{10} (\text{difference in nodule size [mm] between first CT and second CT})}$$

Lung nodule maximum and mean density will be measured by the software lung VCAR (GE) before and after treatment.

Within 6 days an expert radiologist will read the images on the workstation through the windows for lung parenchyma (WW 1500, WL -650) and with MPVR (maximum projection visual resolution) reconstruction and mediastinum windows (WW 400, WL 40). A comparison between first year and baseline CT scan will be performed by Cosmos radiologists. All exams which show persistence of previous identified subsolid lung nodules will be discussed in a specific meeting with a senior radiologist (chemoprevention trial-responsible) and a senior thoracic surgeon (chemoprevention trial-responsible) within 10 days of the CT investigation. Eligible cases for the chemoprevention trial according to the criteria in section 4.1 and 4.2 are scheduled for the preliminary phone contact.

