## 8. CRITERIA FOR EVALUATION AND ENDPOINT DEFINITION

### 8.1 Primary Endpoint

For the purposes of the primary endpoint, only sub-solid (non-solid or partially solid) nodules will be assessed. Target lesions are defined as non solid or partially solid nodules persistent at least after 3 months follow up with standard or low dose CT scan, at least 4 mm in size. Non target lesions include solid nodules (larger than 3.5 mm), new lesions at baseline (e.g., that were not present on prior CT) or non-solid or partially solid nodules < 4mm in size.

The primary end-point will be the difference in sum of longest diameters of baseline target lesions in a person-specific analysis. New subsolid lesions identified during follow-up satisfying the same criteria for the definition of target lesion will also be included in the analysis.

It has been assumed a -0.2 mm average reduction of the sum of the longest diameter of all non-solid and partially-solid lesions at 12 months with respect to baseline in the placebo arm and an expected average reduction of -1.0 mm in the aspirin group.

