## 13. STATISTICAL CONSIDERATIONS

### 13.1 Study Design/Description

The trial will be a randomized double-blind placebo controlled phase IIb study. Patients will be randomized to receive either aspirin 100 mg/day or matched placebo for 1 year. Analysis will be performed according to intention to treat principle and then according to efficacy.

The primary endpoint will be the difference of the sum of longest diameters of subsolid (non-solid or partially solid) lung nodules in a person-specific analysis.

The sample size has been calculated assuming a -0.2 mm average reduction of the sum of the longest diameter of all non-solid and partially-solid lesions at 12 months with respect to baseline in the placebo arm vs. an expected average reduction of -1.0 mm in the aspirin group.

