## 13.2 Randomization/Stratification

In order to keep at minimum the imbalance in treatments a stratified blocked randomization strategy will be used considering only the relevant prognostic factors. Subjects will be stratified according to screening vs non screening CT scan, gender, smoking habits (current versus former smokers) and nodule type (non solid versus partially solid nodules). A blocked randomization will be done within each stratum. Other possible prognostic factors are age, the number of lesions, their volume doubling time and their size but since there is no evidence that they affect the response probability they will be included just in a stratified analysis, not during the randomization process.

Justification of stratification:

Stratification by nodule type and smoking status is planned because both non solid type and active smoking are associated with the risk of developing lung malignancies and their natural history, while stratification by screening vs non screening CT scan, and gender are conservative. The effect of aspirin has been variable in men and women for the prevention of certain conditions.

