## 13.3 Accrual and Feasibility

A sample size of 128 patients (64 per arm) achieve 80% power to detect a difference of -0.8 mm between the null hypothesis that both groups average reduction is -0.2 mm and the alternative hypothesis that the average reduction of target nodules in the aspirin group is -1.0 mm, with estimated effect size of 0.5 (common standard deviations of 1.6 mm) and with a significance level (alpha) of 0.05 using a two-sided two-sample t-test. The average shrinkage in the placebo arm is derived from the Budesonide trial.

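### The primary mm-change test is unadjusted, and the stratified analysis promised for nodule size, number and growth rate is never specified

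*Combined protocol and SAP*

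**What the plan says.** Section 8.1 defines the endpoint in mm: "The primary end-point will be the difference in sum of longest diameters of baseline target lesions in a person-specific analysis". Section 13.4 compares the average one-year change between arms with a t-test and names neither covariates nor randomization strata. It calls the test paired, although it compares two independent groups. Section 13.3 sizes the trial "with a significance level (alpha) of 0.05 using a two-sided two-sample t-test", and the check below uses that reading.

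Section 13.2 stratifies the randomization by screening versus non-screening CT, gender, smoking status and nodule type. It continues: "Other possible prognostic factors are age, the number of lesions, their volume doubling time and their size". These are left out of the randomization because, it says, "since there is no evidence that they affect the response probability they will be included just in a stratified analysis".

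No later section defines that analysis: there are no strata, cut-points, method or status. The mixed models in 13.5 are for secondary endpoints and name arm, visit, smoking history and age, but not size, number or VDT. Section 13.8 states that no subgroup analyses are planned.

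**The concern.** There are two gaps. First, the reason in 13.2 does not fit the primary endpoint. A response probability belongs to the modified RECIST outcome in 8.2, a secondary endpoint on a relative scale (30% shrinkage). The primary endpoint is an absolute change in a sum, and a sum over more or larger nodules has more room to move. Section 4.1.4 admits nodules of 4 to 10 mm with any VDT, and larger ones with VDT above 400 days, with no stated cap on their number. These baseline values can therefore differ widely between participants.

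Second, size, number and VDT are used neither in the randomization nor in any specified analysis. Any part of the mm change that they predict stays in the error term, and a chance imbalance in them between arms of 64 enters the unadjusted estimate. An undefined stratified analysis also leaves the choice of strata and cut-points open until the data are in hand.

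**Working it through.** **1. The plan's own figure.** Inputs from 13.3: difference 0.8 mm, SD 1.6 mm, two-sided alpha 0.05, two-sample t-test, 64 per arm. The effect size is 0.8/1.6 = 0.5. The noncentral t gives 63.77, so 64 per arm, with power 80.1%. The statement "A sample size of 128 patients (64 per arm) achieve 80% power to detect a difference of -0.8 mm" is reproduced.

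**2. Do size and growth rate matter on the mm scale?** At a constant VDT, the one-year diameter change is d × (2^(365/(3 × VDT)) − 1).

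| Diameter | VDT 400 days | VDT 1000 days |
|---|---|---|
| 4 mm | +0.94 mm | +0.35 mm |
| 10 mm | +2.35 mm | +0.88 mm |

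For growing nodules these differences are of the order of the planned 0.8 mm effect. This shows that size and growth rate scale the possible change. It does not show how much of the actual variance they predict.

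**3. What adjustment would buy.** The documents give no R², so a range is assumed. Residual SD = 1.6 × √(1 − R²). The 95% range of the part of the unadjusted estimate due to chance imbalance in the covariates is ±1.96 × 1.6 × √R² × √(2/64).

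| Assumed R² | Residual SD (mm) | Power, 64 per arm | Chance shift (mm) |
|---|---|---|---|
| 0 | 1.600 | 80.1% | 0 |
| 0.05 | 1.559 | 82.1% | ±0.12 |
| 0.10 | 1.518 | 84.1% | ±0.18 |
| 0.15 | 1.475 | 86.1% | ±0.21 |

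The shifts for the three non-zero rows are about 15%, 22% and 27% of the planned 0.8 mm. They are already contained in the standard error of the unadjusted estimate, 1.6 × √(2/64) = 0.28 mm.

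**4. What adjustment costs.** With k covariates that are not balanced by design and N = 128, the variance of the treatment estimate rises on average by the factor 1 + k/(N − k − 3). For k = 3 this is 1 + 3/122 = 1.025. If the three explain nothing, power is 79.2%. The break-even R² is about 0.02. After this charge the last three powers in the table become about 81%, 83% and 85%.

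**5. How large might R² be?** An illustrative model for size and number (all inputs assumed):
- one, two or three nodules with probabilities 0.7, 0.2 and 0.1, diameters 4 to 10 mm;
- mean relative change −3%, with SD 10 to 20%;
- reading error SD 0.5 to 0.8 mm.

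In it, baseline sum and number explain about 0.6 to 2% of the variance in change. In the version whose overall SD is 1.6 mm, the SD of change rises from 1.35 mm with one nodule to 2.33 mm with three. Burden thus widens the spread more than it shifts the mean.

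For prior growth, take one 8 mm nodule with an equal mix of VDT 400, 600 and 1000 days and no growth, and an assumed reading error SD of 0.3 to 0.8 mm per scan. Simulated R² is 0.3 to 2% when the qualifying scans are 3 months apart and 4 to 12% when they are 12 months apart. Annualising a 3-month difference multiplies reading error by about four.

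**The case against.** The strongest reply is that nothing is broken. Randomization makes the unadjusted test valid, chance imbalance is already priced into its standard error and alpha, and a change score already subtracts the baseline sum. Stratifying by nodule type, which 13.2 links to natural history, gives some further balance. A stratified analysis is also not the same thing as a subgroup analysis, so 13.2 and 13.8 do not flatly contradict each other. All of this stands. It limits the point to precision and to an unspecified analysis. It does not remove the point: subtracting baseline does not remove any correlation between change and baseline, and the promised analysis still has no content.

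A reader might infer more than the documents support:
- **That the plan omits these variables from the primary test because it thinks them irrelevant.** The sentence in 13.2 explains their absence from the randomization, reports a lack of evidence, and promises a use in analysis. Section 13.4 gives no reason for having no covariates.
- **That size, number and growth largely determine the mm change.** No correlation or R² is given, and the illustrative R² for size and number is 2% or less.
- **That power would rise from 80% to about 87%.** This comes from the four-VDT mix in step 5, whose changes of 0, +0.70, +1.21 and +1.88 mm have SD 0.69 mm, so 0.69²/1.6² is about 18% of the variance. That mix averages +0.95 mm of growth, whereas 13.1 assumes a mean placebo change of −0.2 mm and 4.1.5 admits nodules that have shrunk by up to 15%. It also treats each growth rate as constant and known without error.
- **That prior growth must be in the model.** The qualifying scans may be only about 3 months apart. The same-procedure rule in section 3 covers months 0 and 12 and does not clearly reach the earlier scan.

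**Conclusion.** The point holds as a recommended improvement. The primary analysis makes no use of baseline variables that the plan itself calls possibly prognostic. The reason given concerns a different endpoint, and the analysis they are assigned to is not specified. There is no bias, no invalid test and no error in the sample size.

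The gain depends wholly on an R² that the documents do not give. It runs from a loss of about one point of power, if three terms explain nothing, to about 86% (85% after the charge for three terms) at R² = 0.15. The illustrative figures for size and number lie at or below the break-even value, so a small gain or none is quite possible. The firmer benefits are an estimate protected against chance imbalance in nodule burden and an analysis fixed in advance.

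**What to change.** In 13.4, replace the t-test with a prespecified ANCOVA of the 12-month sum of longest diameters (or its change) on arm, baseline sum, number of baseline target nodules and the four randomization factors.

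In 13.2, delete the stratified analysis. Alternatively, define it as a sensitivity analysis, with its strata, cut-points and method, and reconcile it with 13.8. Remove the response-probability reason or reword it for the mm endpoint.

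Optionally, prespecify prior growth from the qualifying CTs as a further covariate or as a sensitivity analysis. Express it as log diameter ratio per year, because VDT is undefined for stable nodules and negative for shrinking ones. State how scans close together, or taken with different CT procedures, are handled.

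The cost is SAP wording and a few model terms, fixed before unblinding. Baseline sum and number come from the baseline CT, so no new data are needed. The randomization factors are balanced by design and add little to the variance.

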## 13.3 Accrual and Feasibility

A sample size of 128 patients (64 per arm) achieve 80% power to detect a difference of -0.8 mm between the null hypothesis that both groups average reduction is -0.2 mm and the alternative hypothesis that the average reduction of target nodules in the aspirin group is -1.0 mm, with estimated effect size of 0.5 (common standard deviations of 1.6 mm) and with a significance level (alpha) of 0.05 using a two-sided two-sample t-test. The average shrinkage in the placebo arm is derived from the Budesonide trial.

## 13.4 Primary Objective, Endpoint(s), Analysis Plan

All randomized patients who received at least one dose will be included in the study analysis with an intent-to-treat approach. A secondary analysis will also be carried out after excluding non-compliers and subjects who will drop-out and who will refuse treatment after randomization.

Subject will be considered compliant if at least 80% of the drug has been taken.

Using a more conservative approach, patients who drop-out or have missing final CT scans will be considered in the failure group. Both the intent-to-treat and efficacy analyses will be conducted on a per subject basis. A two-sided paired t-test will be used to compare the average change in the dimension of sub-solid nodules in the aspirin group compared to the placebo group at 1 year.

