## **8.3 Off-Agent Criteria**

Participants may stop taking study agent for the following reasons: completed the protocol-prescribed intervention, adverse event or serious adverse event, inadequate agent supply, noncompliance, concomitant medications, medical contraindication. Participants will continue to be followed, if possible, for safety reasons and in order to collect endpoint data according to the schedule of events. Subjects will not be replaced.

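### Section 13.4 names a paired t-test for aspirin versus placebo, but the arms are parallel and unmatched, and Section 13.3 sized the trial on a two-sample t-test.

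*Combined protocol and SAP*

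**What the plan says.** Section 13.4 is the only place that names the primary test: "A two-sided paired t-test will be used to compare the average change in the dimension of sub-solid nodules in the aspirin group", and the sentence goes on "compared to the placebo group at 1 year". The contrast is therefore between arms, and the quantity compared is already a change.

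Section 13.3 sizes the trial for the same contrast with a different test. It states "A sample size of 128 patients (64 per arm) achieve 80% power to detect a difference of -0.8 mm", and completes the specification "with a significance level (alpha) of 0.05 using a two-sided two-sample t-test". The standardised effect there is 0.5, with a common SD of 1.6 mm.

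Section 13.1 gives the design: "Patients will be randomized to receive either aspirin 100 mg/day or matched placebo for 1 year". The word matched there describes the placebo, not the participants. Section 13.2 uses blocked randomisation within strata formed by four two-level factors: screening or non-screening CT, gender, smoking status and nodule type. The mixed model in Section 13.5 is for secondary endpoints.

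**The concern.** A paired t-test works on differences within defined pairs. Blocks within strata balance the arms, but they do not link one aspirin participant to one placebo participant. An analyst following Section 13.4 literally would have to invent the pairs.

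Three consequences follow.

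- The primary p-value cannot be reproduced from the plan, because it changes with the pairing chosen.
- The 80% power in Section 13.3 belongs to a different test from the one named.
- Equal arms at analysis cannot be assumed. Blocks fill within 2 × 2 × 2 × 2 = 16 strata, and Section 8.3 says "Subjects will not be replaced". Cross-arm pairing would have to drop the surplus participants of the larger arm.

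A second literal reading, baseline against month 12 within each arm, would not compare aspirin with placebo at all.

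**Working it through.** **Inputs.** From Sections 13.1 and 13.3: mean change −0.2 mm on placebo and −1.0 mm on aspirin, common SD 1.6 mm, 64 per arm, two-sided alpha 0.05. Standardised effect d = 0.8 / 1.6 = 0.5. All powers use the noncentral t distribution.

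**1. The plan's own figure.** For the two-sample t-test, the noncentrality is d / √(1/n₁ + 1/n₂) = 0.5 / √(2/64) = 2.828 on 126 df. Power is 80.1%. Solving for 80% gives 63.77, so 64 per arm and 128 in total. Section 13.3 reproduces.

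**2. Was the trial sized on a paired test?** A paired or one-sample test with a standardised effect of 0.5 needs 33.4 pairs, so 34. The figure of 128 does not come from that calculation.

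**3. Arbitrary pairing, equal arms.** The difference between two unrelated participants has SD 1.6 × √2 = 2.263 mm. The standardised difference is 0.8 / 2.263 = 0.354, and the noncentrality is 0.354 × √64 = 2.828, as before, but on 63 df. Power is 79.5%.

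Simulation of 200,000 trials per scenario (64 per arm, SD 1.6 mm, one arbitrary pairing per trial) gave these rejection rates:

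| True difference | Two-sample | Paired | Tests disagree |
|---|---|---|---|
| 0 | 4.9% | 4.9% | 1.1% |
| 0.8 mm | 79.9% | 79.3% | 2.9% |

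**4. Unequal arms.** The documents give no evaluable counts, so these are assumed for illustration. The paired test can use only the smaller arm, with noncentrality 0.5 × √(n_min / 2).

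| Evaluable | Two-sample | Paired |
|---|---|---|
| 60 vs 64 | noncentrality 2.782, df 122: 78.8% | 2.739, df 59: 76.8% |
| 52 vs 62 | noncentrality 2.659, df 112: 75.1% | 2.550, df 51: 70.6% |

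**5. Within-arm reading (worst case).** Suppose aspirin does nothing and both arms change by −0.2 mm. Each within-arm test then has noncentrality (0.2 / 1.6) × √64 = 1.0 on 63 df. The chance of any significant result is 16.6%, and of a significant reduction 16.5%. A significant reduction on aspirin with no significant result on placebo has probability 0.1647 × (1 − 0.1664) = 13.7%. The documents state no such decision rule, so this shows what the reading would cost and is not the type I error of the plan.

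**The case against.** The strongest reply is that this is a slip with an obvious correction. Section 13.3 gives the hypotheses, alpha, sidedness and test for the same contrast, Section 13.1 fixes the parallel design, and the disputed sentence itself compares change between arms. Together they point to an independent two-sample t-test on per-person change, with the word paired most plausibly a stray reference to the baseline-to-month-12 difference. That is probably the intent. It does not settle the matter, because the analysis section is what an analyst follows and it names a different test.

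It is also fair that the measured harm is small: alpha is kept, and equal-arm power falls by only 0.6 points. The case for correction rests on prespecification of the primary test, not on bias.

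The unequal-arm counts are assumptions. Section 8.3 keeps following participants who stop the agent where possible, Section 13.4 places missing final scans in a failure group, and Section 13.6 allows multiple imputation above 5% missing. The 52 vs 62 example has 14 of 128 missing (10.9%), above that threshold. Those rows show direction, not a forecast.

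Finally, changing the test name does not by itself make the analysis fully reproducible. The failure group has no stated value on a millimetre scale, and its relation to imputation is not given. That is a separate issue and needs its own correction.

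**Conclusion.** The concern holds. The primary test as written is undefined for this design and contradicts the sizing section, and no other section names a different primary test. It must be fixed because it is the primary analysis of a randomised trial, even though the numerical effect is modest.

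With 64 evaluable per arm and the plan's effect and SD, arbitrary pairing costs 0.6 points of power and leaves type I error unchanged. In the illustrative unequal arms the cost is 2.0 points (78.8% to 76.8%) and 4.5 points (75.1% to 70.6%). The sample size in Section 13.3 is correct for the test it names.

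**What to change.** **Required.** Replace the test sentence in Section 13.4 with wording such as:

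> The primary comparison is a two-sided independent two-sample t-test (alpha 0.05) of the per-subject change from baseline to month 12 in the sum of longest diameters, aspirin versus placebo.

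This is the test Section 13.3 already assumes, so N stays at 128 and the stated 80% power, at 64 evaluable per arm, then belongs to the named test. The cost is one sentence, with no change to data collection or budget.

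**Optional.** In the same edit, the primary analysis could become an ANCOVA of the same change on arm, baseline sum and the four randomisation factors, with the two-sample t-test kept as the sensitivity analysis and the conservative basis for N. Leaving these covariates out is conservative, not invalid. The five covariates reduce the df from 126 to 121, which costs less than 0.1 point of power if they predict nothing (80.15% to 80.12%). Any gain depends on their multiple correlation r with the change, which the documents do not give. With noncentrality 2.828 / √(1 − r²), power is 80.5% at r = 0.1, 81.7% at 0.2, 83.7% at 0.3, 86.5% at 0.4 and 90.0% at 0.5.

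If this is adopted, Section 13.4 should say how it relates to the plan in Section 13.2 for age, lesion number, volume doubling time and size, of which it says "they will be included just in a stratified analysis, not during the randomization process".
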